
 • Acute Care: Inpatient (IP) stays for acute care at a medical center lasting ≥24 hours. • Extended Care: IP stays in VA community centers and care in VA nursing homes. 
Datasets within acute and extended care
 
 • Main: Hospital IP stay. Example variables include: 
 ○ 1^o/2^o diagnosis ○ Length of stay • Bed: IP stay under a specified physician service. Example variables include: 
 ○ 1^o/2^o diagnosis ○ Admission and discharge date ○ Length of stay • Procedure: Procedure in IP stay. Example variables include: 
 ○ Procedure date ○ ICD-9/10-CM codes • Surgery: Surgery in IP stay. Example variables include: 
 ○ Surgery date ○ ICD-9/10-CM codes 	
 • Event: One ambulatory/outpatient encounter by a patient. Example variables include: 
 ○ Encounter date ○ Procedure codes ○ Diagnosis codes 	
 • Laboratory results: Results for a specific list of laboratory tests, inpatient and outpatient. Example variables include: 
 ○ Service date ○ Result value ○ Test unit • Pharmacy: Prescription utilization and costs, inpatient and outpatient. Example variables include: 
 ○ Dispensing date ○ Quantity ○ Days supply ○ Cost 	
 • Discharge: Costs for inpatient services at discharge. Example variables include: 
 ○ Admission and discharge date ○ Length of stay ○ Total cost • Outpatient: Costs for outpatient services. Example variables include: 
 ○ Primary diagnosis ○ Visit date ○ Total cost 	
 • National repository of VHA administrative and clinical data. • Vital signs information such as blood pressure, height, weight, etc. • Example variables include: 
 ○ Vital type ○ Result ○ Date taken and entered 	
 • Provides mortality information. • One record per person who has received care or benefits, or enrolled in the VHA. • Provides enrolment information for each patient. • Example variables include: 
 ○ Death date ○ Race ○ Sex

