Claim gaps	Truven: Outpatient pharmacy claims table VHA: Pharmacy file	The average gap between prescription fills of insulins will be calculated in the pre- and post-index periods among all the study cohorts.
Concomitant medications ^{18,19,20}	Truven: Outpatient pharmacy claims table VHA: Pharmacy file	A flag will be created for patients prescribed antihyperglycemic agents (AHA): thiazolidinediones, sulfonylureas, biguanides, meglitinides, alpha-glucosidase inhibitors, DPP-4 inhibitors, bile acid sequestrants, fixed-dose combinations, GLP-1 receptor agonists, and amylin agonists (Appendix 1).

[2018-7241 Study Identifier] Observational Study Protocol

HbA1c ²¹	VHA: Lab file	The HbA1c value in the baseline and follow-up period for each index event will be reported. Baseline HbA1c (pre-index HbA1c) will be the HbA1c measurement -90/+30 days of the index date. For patients with multiple HbA1c measurements within this period, the measurement taken closest to the index event date will be reported as the baseline HbA1c value. The follow-up HbA1c value will be the HbA1c measurement taken furthest in the time period after the 30 day-post index event date. However, based on the sample size, HbA1c within 2 months prior to the end of the study follow-up will be considered as the post-index HbA1c.
Hypoglycemic events	Truven: Inpatient service table, outpatient service table VHA: Inpatient and outpatient files, Lab file and Pharmacy file	Hypoglycemia events in the pre-index and post-index period will be evaluated using the ICD-9 codes from the Ginde algorithm (Appendix 1) ²² or the presence of a cutoff of blood glucose ≤ 70 mg/dL, or any evidence of intramuscular glucagon administration (Appendix 1). Hypoglycemia event occurred on or after the index date will be considered as the follow-up hypoglycemia event; and hypoglycemia event occurred on or prior to - 1 day of the index date will be considered as the baseline hypoglycemia event. Number of hypoglycaemia events per patient per year (PPPY) will be reported in both the pre-index and post-index periods.
Prescribed TDD	Linked Truven claims and EMR data:	The prescribed physician TDD will be calculated, and will be reported both as continuous and categorical variable.

[2018-7241 Study Identifier] Observational Study Protocol

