Zero-inflated negative binomial mixed model will be used to evaluate factors associated with number of hypoglycemia events PPPY in the pre- and post-index periods among U-500R syringe initiators, U-500R Kwikpen initiators, and U-500R device switchers. Zero-inflated negative binomial distribution is a mixture of a binary distribution that is degenerate at zero and an ordinary count distribution such as negative binomial. In cases of outcome variable being repeatedly measured from the individual subjects, zero inflated models are extended to include random effects to account for the correlation among the repeated measures within a subject. In the current model, the number of hypoglycemia events which might have more zeroes (for example not every patient might have a lab visit for glucose) and is measured at two time intervals (before and after the index event; U-500R initiation/device switch), will be considered the dependent variable. Observed TDD, and HbA1c will be considered as the time varying covariates in the model (measured both in the before and after index date), and the time-independent covariates will include the demographic and clinical characteristics.

The complete list of covariates will include:

- age
- sex
- race
- BMI
- baseline CCI score

[2018-7241 Study Identifier] Observational Study Protocol

- observed TDD from claims
- HbA1c
- time (pre/post)

Note: Age, sex, race, BMI, and CCI score will be assessed during pre-index period. Observed TDD and HbA1c will be calculated during the entire pre-index and post-index periods, respectively. Pre-index HbA1c will be defined as the HbA1c measurement -90/+30 days of the index date. For patients with multiple HbA1c measurements within this period, the measurement taken closest to the index event date will be reported as the pre-index HbA1c value. Post-index HbA1c will be defined as the HbA1c within 2 months of the end of the follow-up period.

Research Objective 2: Secondary Objective 2bDescriptive Analysis

Treatment outcomes (HbA1c and number of hypoglycemic events) and prescriber behavior (observed TDD in claims and prescribed TDD from the physician) will be analyzed descriptively and quarterly before and after U-500R syringe initiation and U-500R Kwikpen initiation, and before and after U-500R device switch from syringe to Kwikpen.

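### The before/after hypoglycemia comparison counts laboratory lows without regard to how many glucose tests were done, so a change in testing between periods would move the composite rate in proportion to its lab-detected share

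*Protocol*

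**What the plan says.** Section 5.5, Table 3 defines a hypoglycemia event by a diagnosis code, "or the presence of a cutoff of blood glucose ≤ 70 mg/dL, or any evidence of intramuscular glucagon administration". The sources it names are the Truven service tables and, for the other database, "VHA: Inpatient and outpatient files, Lab file and Pharmacy file". Figure 4 in Section 5.2 describes the VHA laboratory extract as "Results for a specific list of laboratory tests, inpatient and outpatient". The rate uses calendar time: "Number of hypoglycaemia events per patient per year (PPPY) will be reported in both the pre-index and post-index periods". Events on the index date belong to follow-up.

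For Secondary Objective 2a, Section 6.4.1 plans a paired t-test or McNemar's test and then a regression: "Zero-inflated negative binomial mixed model will be used to evaluate factors associated with number of hypoglycemia events PPPY". The rationale describes the outcome as "the number of hypoglycemia events which might have more zeroes (for example not every patient might have a lab visit for glucose"). The list headed "The complete list of covariates will include" contains age, sex, race, BMI, baseline CCI score, observed TDD, HbA1c and time. Of these, only TDD, HbA1c and time change within a patient. No item measures glucose testing.

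Section 7.1 names hypoglycemia as the protocol-defined adverse event and identifies it, in both periods, by the ICD-9 codes alone.

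**The concern.** A laboratory low can be seen only if a glucose test was done. The number of lab-detected events is therefore the number of tests multiplied by the chance of a low value per test. If a patient is tested more, or less, after index than before, the count moves even when the underlying risk does not. The planned contrast cannot tell the two apart.

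The protocol sees that testing is uneven but treats this as a question of excess zeros. Zero inflation can represent patients who are never tested. It does not correct a change between periods in how often tested patients are tested.

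Hypoglycemia is the only adverse event that the protocol defines. More testing after index would look like harm, and less testing could hide it.

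**Working it through.** The protocol gives no hypoglycemia rate, testing frequency or expected effect, so there is no figure of its own to reproduce. The check has four steps.

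**1. How a testing change passes through.** Let C be the rate of coded or glucagon events before index, T the number of glucose tests, and p the chance of a low value per test. The baseline composite is C + T·p, and the lab-only share is s = T·p / (C + T·p). If C and p stay the same and tests change by a factor k, the apparent post/pre ratio is

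(C + k·T·p) / (C + T·p) = (1−s) + s·k.

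Every patient has 9 months on each side, so the annual rate is the count divided by 0.75 in both periods, and the ratio is unaffected. Both s and k are assumed here:

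| s | k = 0.8 | k = 1.0 | k = 1.2 | k = 1.5 | k = 2.0 |
|---|---|---|---|---|---|
| 0.25 | 0.95 | 1.00 | 1.05 | 1.125 | 1.25 |
| 0.50 | 0.90 | 1.00 | 1.10 | 1.25 | 1.50 |
| 0.75 | 0.85 | 1.00 | 1.15 | 1.375 | 1.75 |

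For example, s = 0.5 and k = 1.5 give 0.5 + 0.5 × 1.5 = 1.25.

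**2. The paired t-test.** A simulation with no true change in risk used 400 runs per setting. It assumed 0.12 events per 9 months, a mean of 3 tests per tested patient before index, 10% of patients never tested, and risk varying between patients. The largest n, 4,066, is the Table 4 count of Kwikpen patients with at least two HbA1c values, before the other selection criteria.

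| n | s | False positives, k = 1.2 | False positives, k = 1.5 |
|---|---|---|---|
| 1,000 | 0.5 | 11% | 44% |
| 1,000 | 0.75 | 19% | 78% |
| 4,066 | 0.5 | 29% | 97% |
| 4,066 | 0.75 | 61% | 100% |

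At k = 1.0 the rate was 4–6% over all sample sizes tried (500 to 4,066), as it should be. Comparing lab-detected events per test gave about 1.5–6% over the same sample sizes and k from 1.0 to 1.5.

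**3. Zero inflation.** A simplified zero-inflated negative binomial model (constant zero part, no random effects) was fitted to 15 simulated data sets. These had n = 4,000, 30% never tested, 0.3 events per 9 months, s = 0.75 and k = 1.5, again with no true change. The fitted time effect was a rate ratio of 1.41. The raw ratio in the same data was also 1.41; the formula gives 1.375, and the gap is simulation noise. The zero-inflated part removed none of the shift. The planned model also has random effects, which this check left out.

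**4. Is unequal testing plausible under the protocol's own rules?** Section 5.3.1 requires an HbA1c more than 30 days after index. It lets the baseline HbA1c fall anywhere from 90 days before to 30 days after index. A patient can therefore enter with no laboratory draw before index, but never without one after it. Table 3 also places index-date events in follow-up, so a low value in blood taken on the day of initiation counts as post-index. An HbA1c draw is not a glucose test, so this makes unequal laboratory contact plausible without showing that it occurs.

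**The case against.** Several points on the other side are sound.

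- A reader might infer that any testing change is reported in full as a change in hypoglycemia. It is not: the outcome is a composite, and only the lab-detected share carries the change.
- A reader might infer that untested patients scored as zero, or often-tested patients with many events, bias the comparison by themselves. They do not. Stable testing habits are present in both periods of a paired contrast, and the model has patient-level random effects. Only a within-patient change between periods matters.
- A reader might infer that the protocol has no laboratory-free definition. Section 7.1 has one, based on codes, covering both periods and summarised in the report. It is there for adverse-event reporting, however, and is not named as a companion to the Objective 2a comparison.
- Nothing in the protocol shows that testing changes at initiation or device switch, or in which direction.
- Table 3 names a laboratory file for VHA only, although Section 5.2 lists laboratory results for LCED. The share s may differ between databases.
- How several low values on one day or in one admission are counted is not stated. A plan not at hand may settle that, so it is not part of this point.
- A test-count offset is not a clean cure. Tests ordered because of symptoms carry information about risk, and dropping periods without a test breaks the pairing.

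The core remains. The protocol itself fixes the event definition, the calendar-time rate, the unadjusted paired tests and a covariate list that it calls complete, and none of them accounts for testing.

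**Conclusion.** The point holds as a gap in the Objective 2a comparison. A within-patient change in glucose testing would shift the composite rate by the factor (1−s) + s·k, and neither the paired tests nor zero inflation removes it. With s between 0.25 and 0.75 and k between 0.8 and 1.5, all assumed, the apparent ratio runs from 0.85 to 1.375 with no change in risk. These figures also assume that the chance of a low value per test and the rate of coded or glucagon events stay constant.

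The documents do not support the stronger reading that the result will be biased, or biased upward. Size and sign are unknown, and the plan as written would not reveal them. Separately, Table 3 and Section 7.1 define hypoglycemia differently, which is a plain inconsistency. The objective is secondary, but it carries the only defined adverse event, so the change should be made.

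**What to change.** 1. Reconcile the hypoglycemia definitions in Table 3 and Section 7.1, and state which one each analysis uses.
2. Keep the composite. In Objective 2a, also run the before/after comparison and the model for clinically recognised events (diagnosis code or glucagon), separately from lab-detected events.
3. Tabulate glucose tests per patient before and after each index event, by database.
4. Add a supportive analysis of the lab-detected component that accounts for test count, with the caveat that symptom-driven testing is informative.
5. State in advance that a change in the composite is read as a change in hypoglycemia only if the code/glucagon component agrees or testing is similar in both periods.

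The cost is small: revised wording, some extra analysis, and a test count from the laboratory data already in use. The code/glucagon component will have fewer events than the composite and so less precision. It also depends on patients being seen, so it limits the surveillance problem without removing it.

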- ❖ **Primary Objective 1:** Evaluate the treatment patterns of insulin including observed total daily dose [TDD] in claims, adherence, prescription fill rate, claim gaps, persistence and concomitant medication use among T2DM patients before and after U-500R syringe initiation and U-500R Kwikpen initiation separately as well as before and after U-500R device switch from syringe to Kwikpen:
 - Characterize U-500R Kwikpen patients;
 - Determine differences between treatment patterns before and after U-500R Kwikpen initiation;
 - Determine differences between treatment patterns before and after U-500R syringe initiation; and
 - Determine differences between treatment patterns before and after U-500R device switch from syringe to Kwikpen.

Research Objective 2: Treatment Outcomes

- ❖ **Primary Objective 2:** Evaluate the HbA1c level among T2DM patients before and after U-500R syringe initiation and U-500R Kwikpen initiation separately, as well as before and after U-500R device switch from syringe to Kwikpen:
 - Determine differences between HbA1c level before and after U-500R Kwikpen initiation;
 - Determine differences between HbA1c level before and after U-500R syringe initiation;
 - Determine differences between HbA1c level before and after U-500R device switch from syringe to Kwikpen; and
 - Determine whether observed TDD in claims or insulin adherence played a role in HbA1c changes among U-500R syringe initiators, U-500R Kwikpen initiators, and device switchers from syringe to Kwikpen.
- ❖ **Secondary Objective 2a:** Evaluate the hypoglycemic events among T2DM patients before and after U-500R syringe initiation and U-500R Kwikpen initiation separately, as well as before and after U-500R device switch from syringe to Kwikpen:
 - Determine differences between hypoglycemia events before and after U-500R Kwikpen initiation;
 - Determine differences between hypoglycemia events before and after U-500R syringe initiation;

[2018-7241 Study Identifier] Observational Study Protocol

- Determine differences between hypoglycemia events before and after U-500R device switch from syringe to Kwikpen; and
 - Determine whether observed TDD in claims or insulin adherence played a role in hypoglycemic events among U-500R syringe initiators, U-500R Kwikpen initiators, and device switchers from syringe to Kwikpen.

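### Secondary Objective 2a has no planned analysis of adherence and hypoglycemia, and its only adjusted model conditions on post-index HbA1c, so the time coefficient is not the total before/after change

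*Protocol*

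**What the plan says.** Section 4.1, Secondary Objective 2a, has four parts. Three ask for a before/after comparison, one per cohort, for example: "Determine differences between hypoglycemia events before and after U-500R Kwikpen initiation". The fourth is explanatory and covers all three cohorts: "Determine whether observed TDD in claims or insulin adherence played a role in hypoglycemic events among U-500R syringe initiators".

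Section 6.4.1 plans two things for this objective:

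- **Descriptive analysis.** Events before and after the index event are compared with a paired t-test, or McNemar's test for categorical variables, without covariates.
- **Multivariate analysis.** "Zero-inflated negative binomial mixed model will be used to evaluate factors associated with number of hypoglycemia events PPPY in the pre- and post-index periods". The number of events is named as the dependent variable. The covariates are introduced with "The complete list of covariates will include" and are age, sex, race, BMI, baseline comorbidity score, observed total daily dose (TDD), HbA1c and time. TDD and HbA1c vary with time: "Observed TDD, and HbA1c will be considered as the time varying covariates in the model".

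The note under that list places post-index HbA1c in the last 2 months of follow-up. Table 3 (Section 5.5) counts follow-up hypoglycemia from the index date.

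**The concern.** There are two separate problems.

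First, the fourth part of the objective names adherence, but the model that should serve it contains no adherence term and nothing else takes its place. Because the list is declared complete, an analysis plan that added adherence to this model would contradict the Protocol.

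Second, HbA1c is the outcome of Primary Objective 2, and Section 3 cites evidence that it improves when patients move from U-100 to U-500R. A variable that the index event can change lies on the path from that event to hypoglycemia. With it in the model, the time coefficient compares the two periods at equal HbA1c, not as patients experienced them. TDD raises the same question of interpretation, although the objective does ask about TDD.

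Hypoglycemia is the only adverse event that Section 7.1 collects, and this is its only adjusted model. A time effect near 1 could be read as reassurance when it means only that nothing remains after HbA1c is held fixed.

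**Working it through.** The Protocol gives no event rate, effect size or power for hypoglycemia, so there is no figure to reproduce. The first two steps compare sections; the rest illustrate size with assumed inputs.

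**1. Where adherence is analysed (Section 6.4.1)**

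| Outcome | Adherence as covariate | Reason given | Mediation analysis |
|---|---|---|---|
| HbA1c (Primary Objective 2) | No | Collinearity with time | Yes |
| Costs (Primary Objective 3) | No | Collinearity with time | Yes |
| Hypoglycemia (Secondary Objective 2a) | No | None | None |

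Primary Objective 1 models adherence as an outcome. Secondary Objective 2b concerns observed and prescribed dose and has no multivariate analysis. No planned analysis links adherence to hypoglycemia.

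**2. Timing**

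Follow-up is 9 months and the HbA1c window is its last 2. The part of follow-up before the window opens is (9 − 2)/9 = 0.78. If events occur at a constant rate (assumption), about 78% of them precede the HbA1c value meant to explain them.

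**3. What the time coefficient leaves out**

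Suppose a log-linear count model in which the index event acts on hypoglycemia only through HbA1c. The total post/pre rate ratio is then exp(b × d), where b is the log-rate slope per HbA1c point and d is the HbA1c change. The time coefficient adjusted for HbA1c corresponds to a rate ratio of 1. Neither b nor d is in the Protocol. Over assumed values:

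| b | d = −0.3 | d = −0.6 | d = −1.0 |
|---|---|---|---|
| −0.1 | 1.03 | 1.06 | 1.11 |
| −0.2 | 1.06 | 1.13 | 1.22 |
| −0.3 | 1.09 | 1.20 | 1.35 |

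**4. Simulation check**

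Inputs, all assumed: 4,000 patients, two periods of 0.75 years, slope −0.25, HbA1c fall 0.8, no direct effect, 20 runs. A Poisson model with patient clustering was fitted with and without HbA1c. The true conditional rate ratio is exp(0.25 × 0.8) = 1.22.

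- Time effect without HbA1c: 1.24. It slightly exceeds 1.22 because the simulated HbA1c change varied between patients (SD 0.7): 1.22 × exp(0.25² × 0.7²/2) = 1.22 × 1.015 = 1.24.
- Time effect with HbA1c: 1.00.
- With an unmeasured patient factor that both lowers HbA1c and raises event risk: 1.24 without HbA1c and 0.91 with it, an apparent reduction while events rise.

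This model is simpler than the planned zero-inflated mixed model. It shows the mechanism and does not predict the study's result.

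**5. Lost records**

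The selection criteria (Section 5.3.1) require an HbA1c at some time after day 30; having one in the last 2 months is only flagged. A patient tested in month 5 but not later is eligible, yet has no post-index HbA1c under the 2-month rule, and that patient's post-index record leaves the model. If tests come every 90 to 180 days (assumption), the share without a value in the last 61 days is 1 − 61/90 = 0.32 to 1 − 61/180 = 0.66.

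**The case against.** The strongest reply is that the objective is largely served. The paired comparisons take up all three before/after bullets without conditioning on HbA1c, and TDD is in the model. The model's stated purpose is to "evaluate factors associated with number of hypoglycemia events PPPY in the pre- and post-index periods", so its time coefficient is not declared to be the effect of U-500R. All of this stands. A reader might infer that the plan cannot answer Secondary Objective 2a, or that it conceals a rise in hypoglycemia. The documents support neither: the paired comparisons would show a rise, and only the adherence half of one bullet is without an analysis.

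Three further readings also go too far:

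- **That the outcome is invalid because a yearly rate is not an integer** (one event in 9 months becomes 12/9 = 1.33). The same paragraph names the number of events as the dependent variable, and both periods are fixed at 9 months. The rate wording is loose, not a modelling error.
- **That patients without a late HbA1c drop out of the safety analysis.** They lose the post-index record in this model. A mixed model can keep the pre-index record, and the paired comparisons do not use the window. The window is also not settled: Table 3 takes the latest value after day 30 and makes the 2-month rule depend on sample size, while the model's note gives the rule without condition.
- **That the adjusted estimate must understate harm.** This requires HbA1c to fall. Section 3 cites a fall for moves from U-100 to U-500R but gives none for device switchers.

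The Protocol's collinearity argument could also be used against placing adherence beside time in one model. That explains leaving it out as a covariate. It does not explain the missing mediation analysis, which is the Protocol's own answer to that problem for the other two outcomes.

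**Conclusion.** The point holds in two parts. That no planned analysis addresses adherence and hypoglycemia follows directly from the text and needs no assumption. That the adjusted time coefficient is not the total before/after change follows from including a covariate that the index event may change; it matters to the extent that HbA1c does change and is related to event risk. The late measurement window makes the coefficient harder to interpret and removes some post-index records.

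The size cannot be derived from the Protocol. The range of 1.03 to 1.35 rests on assumed slopes of −0.1 to −0.3 per point, assumed HbA1c falls of 0.3 to 1.0 points, and no direct effect. The 32% to 66% of patients without a late HbA1c rests on an assumed testing interval. The change should be made, because otherwise part of a stated objective goes unanswered and the only adjusted safety estimate is open to misreading.

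**What to change.** 1. Make the main adjusted model for Secondary Objective 2a the event count on time plus baseline covariates, without post-index HbA1c or TDD.
2. Add an analysis of the role of TDD and adherence. One option is a second model that adds TDD and the proportion of days covered, with their collinearity with time reported. The other is a mediation analysis parallel to those for HbA1c and costs, stating the effect scale and that patients are the resampling unit.
3. Keep the HbA1c-adjusted model as a labelled exploratory analysis, and make its post-index HbA1c window agree with Table 3.

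The cost is one or two extra models on data already held. Mediation with a zero-inflated count outcome takes more programming than the linear HbA1c case, so the second model is the cheaper choice. The main model keeps post-index records that the present model would lose.
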